5.0 DOSE MODIFICATION FOR TOXICITY

5.1 Dose Limiting Toxicity (DLT)

A DLT is defined as a clinically significant adverse event or abnormal laboratory value assessed as unrelated to disease progression, intercurrent illness, or concomitant medications and meets any of the criteria below. Any DLT must be a toxicity considered at least possibly related to pamiparib (BGB-290) or TMZ.

ABTC # 1801

NCI # ABTC-1801

PI: [name]

Dose limiting toxicities (treatment related) are defined below. Dose limiting toxicities must have an attribution of possible, probable, or definite to pamiparib (BGB-290) or TMZ. For patients experiencing a DLT, pamiparib (BGB-290) and TMZ will be stopped. If the patient recovers (\leq grade 1 [or tolerable grade 2 for non-hematologic toxicity] or \leq baseline), refer to the Toxicity Management Table below for instruction on whether a dose reduction of TMZ or pamiparib (BGB-290) is required for subsequent doses, or whether pamiparib (BGB-290) and TMZ must be permanently discontinued. Skipped doses will not be made up. If there is any question or confusion concerning a DLT, the treating site should contact the ABTC Central Office to determine patient's DLT status. The ABTC Central Office, with the Study Chair, will make the final decision.

- → Hematological toxicities will be considered dose limiting if any of the following occur and complete blood counts and differentials were obtained according to the mandated schedule (CBC, differential, and platelets drawn twice a week until the ANC ≥ $1500/\mu$ L and platelets ≥100,000/µL): grade 3 or 4 lymphopenia will not be considered a DLT.
 - Grade 4 Neutrophil count decreased (ANC of $< 500/\mu$ L)
 - Grade 4 Platelet count decreased (Platelets $< 25,000/\mu$ L)
 - Grade 3 or 4 Febrile neutropenia
 - Any hematological toxicity that prevents administration of > 80% of the planned TMZ doses for the first cycle

Non-hematological toxicities will be considered dose limiting if any of the following occur:

- Grades 3-4 seizure or intracranial hemorrhage
 - All other grade 3 neurologic toxicity (other than seizure/intracranial hemorrhage) responding *within 3 days* to steroids, anticonvulsants, or electrolyte correction will not be considered dose limiting.
- Grades 3-4 severity with the following exceptions:
 - o except nausea, vomiting, and diarrhea without sufficient prophylaxis *lasting* ≤3 *days*;
 - except alopecia;
 - except grade 3 hyperglycemia;
 - except grade 3 electrolyte disturbances that are asymptomatic and that respond to replacement therapy *within 3 days*;
 - A subject's first episode of deep venous thrombosis (DVT) or pulmonary embolism (PE) will not require dose modification (not a DLT).

ANY DLT (AS DEFINED ABOVE) CAUSING DELAY IN TREATMENT OF OVER 21 DAYS (OR OVER 14 DAYS FOR GRADE 3 HEPATIC TOXICITY) WITHOUT RECOVERY TO $A \leq$ GRADE 1 OR BASELINE STATUS WOULD RESULT IN TAKING THE PATIENT OFF TREATMENT.

ABTC # 1801

NCI # ABTC-1801

PI: [name]

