IDH1/2 mutations in all grades and sub-types of gliomas are presented in Fig. 14, which is taken from a comprehensive review on this subject ⁴⁹. Another factor is likely to have even further reduced the proportion of IDH1/2-mutant tumors that have been tested in clinical trials with PARP inhibitors: most studies specifically excluded secondary GB and/or tumors with features suggestive of components arising from lower grade gliomas. For example, a Phase II/III randomized Alliance trial (A071102; NCT02152982) is

ABTC # 1801

NCI # ABTC-1801

PI: [name]

testing the efficacy of the PARP inhibitor, veliparib, in combination with adjuvant temozolomide in newly diagnosed GB, but it specifically excludes GBs with oligodendroglial features with a 1p19q co-deletion; these tumors commonly harbor IDH1 mutations ⁵⁰. As another example, the aforementioned Oparatic Trial in recurrent GB specifically excludes secondary GB ⁵¹. Collectively, these findings suggest that the target glioma population in whom PARP inhibitors have been tested thus far may not have been the optimal experimental cohort. Instead, an ideal group would be composed of patients with IDH1/2-mutant gliomas, and the proposed trial will test this specific group of patients.

Since the initial concept for this trial was developed, additional information regarding the combination of pamiparib (BGB-290) and TMZ has become available. BGB-290-104, a phase I study for patients with first recurrence of glioblastoma, utilized our proposed dose level 1 of pamiparib (BGB-290) 60 mg twice daily and TMZ 40 mg Days 1-21 every 28 days and found this combination exceeded MTD because of neutropenia and thrombocytopenia. Similarly, BGB-290-103, a solid tumor study using the same pamiparib (BGB-290) schedule with TMZ 40 mg daily, noted excessive hematologic toxicity. Both of these studies have de-escalated TMZ to 20 mg daily.

Pre-clinical data supporting the activity of the PARP inhibitor Pamiparib (BGB-290)

As presented above, we have already confirmed that pamiparib (BGB-290) is active against IDH1/2-mutant versus WT cells. However, pamiparib (BGB-290) also has

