4.1.1 Dose Finding

Pamiparib (BGB-290) will be given at 60 mg BID at each dose/schedule; the dose of TMZ will be de-escalated/changing the treatment schedule, as shown in the table below if necessary:

Dose Level	Pamiparib (BGB-290)	Temozolomide Dose/Schedule
1 (starting dose)	60 mg BID	20 mg QD Days 1-28
-1	60 mg BID	20 mg QD Days 1-21
-2	60 mg BID	20 mg QD Days 1-14
-3	60 mg BID	20 mg QD Days 1-7

Phase I dose/schedule de-escalation

*Pamiparib (BGB-290) will be dose reduced only after discussion with Study Chair

The standard 3+3 design will be used for dose finding. Three patients will be enrolled per dose/schedule cohort. If no DLTs are observed in the first 3 patients at Dose Level 1, 3 additional patients will be enrolled at Dose Level 1 before pursuing Phase II of the protocol. If 1/3 of the patients develops a DLT during the first 4 weeks of treatment beginning from the first dose of pamiparib (BGB-290), Dose/Schedule Level 1 (or any subsequent dose/schedule level) will be expanded by 3 additional patients at the same dose/schedule level. The 3 additional patients must be followed for at least 4 weeks and toxicity evaluated before continuing.

Number of Patients with DLT at a Given Dose/Schedule	Decision Rule
0 out of 3	Enter 3 more patients at the same dose/schedule
1 out of 3	Enter 3 more patients at the same dose/schedule
2 out of 6	This is the maximum tolerated dose/schedule
2-3 out of 3, or \geq 3 out of 6	MTD exceeded, enter 3 patients at next lower dose/schedule

Dose-limiting toxicity (DLT) is defined in Section 5.1. No intra-patient dose escalation is allowed. Patients will be evaluable for the cohort if they have completed at least 80% of their expected dose of pamiparib (BGB-290) for the first treatment cycle (28 days). Patients who experience a DLT will be evaluable for the cohort if they have received at least one dose of pamiparib (BGB-290). The toxicity evaluation period is the first 4 weeks of treatment.

The target DLT rate is 33%. If the MTD is not reached among the pre-specified doses/schedules, the dose for the Phase II portion will be the highest dose/schedule studied for which the DLT rate is \leq 33% in 6 evaluable patients.

ABTC # 1801

NCI # ABTC-1801

PI: [name]

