9– If ANC < 1500 or plts < 100,000, CBCs/differentials will be repeated twice a week until counts are recovered (ANC ≥1500 or plts ≥100,000) per protocol. If counts are recovered (ANC ≥1500 or plts ≥100,000) on day of scheduled drawing do not repeat until next protocol schedule day

10 - Adverse Events must be followed for at least 30 days from last dose of pamiparib (BGB-290).

11-Perform within +14 days of the 30-day post-last dose date.

12– Archived tumor tissue from a prior resection for glioma, preferably from the initial diagnosis, will be collected from all patients. See Section 9.5.1.

 $13\!-\!\pm 1~day$

14-Perform within minus 7 days of first dose

ABTC # 1801

NCI # ABTC-1801

PI: [name]

15- In subjects whose CBC, Diff, Platelets have been stable through the first 6 cycles, the frequency of hematologic testing can be reduced to a q2 weeks schedule (Day 15 of every cycle and Pre-cycle evaluation) starting in Cycle 7. CBC, Diff, Platelets will be considered "stable" if the following criteria are met: 1) No reports of ANC<1500/µl in ANY of the Cycles 1-6 weekly Labs and 2) No reports of Platelets<100,000/µl in ANY of the Cycles 1-6 weekly Labs and 2) No reports of Platelets<100,000/µl in ANY of the Cycles 1-6 weekly Labs. If at any point during treatment on the revised q2 weeks schedule the above mentioned ANC and Platelets criteria are not met, CBC, Diff, Platelets should be repeated twice a week until counts are recovered (ANC ≥1500 or Platelets ≥100,000). Once counts are recovered, the schedule of CBC, Diff, Platelets should go back to, and stay at, weekly monitoring (NOT q2 weeks).

IMPORTANT: The guidance below is subject to applicable local Institutional Policy on telemedicine. In the event that local Institutional Policy regarding telemedicine differs from this guidance, then please follow local Institutional Policy.

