11.0 STATISTICAL CONSIDERATIONS

Phase I /Dose Finding

The primary objective of the phase I study is to determine the safety combination treatment of pamiparib (BGB-290) given at a fixed dose level of 60 mg BID with TMZ 20 mg starting at the dose level/schedule 1 (Days 1-28), then subsequently dose level -1 (Days 1-21), dose level -2 (Days 1-14), and dose level -3 (Days 1-7) in patients with recurrent gliomas and IDH1/2 mutations. The standard 3+3 design will be used for dose finding. Three patients will be treated in a dose/schedule cohort and dose deescalation/changing treatment schedule, if required will take a stepwise fashion with expansion to a total of 6 patients at a putative MTD/ or highest safe dose/schedule. The target DLT rate is 33%.

The MTD is defined as the combination regimen that yields a DLT rate less than, or equal to 33%.

The safety evaluation period is 28 days (the first cycle of treatment) for dose escalation decisions. All safety and toxicity will be followed and data will be collected till 90 days after discontinuation of the treatment.

NCI Common Terminology Criteria for Adverse Events (CTCAE) version 5.0 will be used for scoring toxicity and adverse events. The severity and frequency of toxicity will be tabulated by the tested doses using descriptive statistics. The proportions of subjects who experienced grade 3 or above toxicities will be estimated, along with 95% confidence intervals by each type of toxicity.

ABTC # 1801

NCI # ABTC-1801

PI: [name]

The Phase II efficacy study will be warranted after a safe combination regimen is deemed.

Phase II/ Safety and Efficacy

The primary objective of the phase II portion of the study is to estimate treatment effect in terms of tumor radiographic response in two different patient populations independently. One is a poor risk patient population, alkylator resistant/alkylatorrefractory: Arm A. The other is favorable risk patients who had one distant alkylator failure: Arm B.

Primary Endpoint:

The primary endpoint for both Arm A and B is tumor radiographic response (CR+PR) using Response Assessment in Neuro-Oncology (RANO) criteria by measurable disease.

Study Design /Sample Size:

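### Section 5.1 lets an observed cycle 1 grade 4 neutropenia, grade 4 thrombocytopenia or febrile neutropenia drop out of the 3+3 count if the mandated CBCs were not completed

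*Combined protocol and SAP*

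**What the plan says.** Section 5.1 opens its hematologic DLT list with a two-part test. A toxicity is dose limiting "if any of the following occur and complete blood counts and differentials were obtained according to the mandated schedule". The parenthesis that follows describes the schedule as "CBC, differential, and platelets drawn twice a week until the ANC" and platelets recover. Four criteria sit under this lead-in: grade 4 neutropenia, grade 4 thrombocytopenia, grade 3 or 4 febrile neutropenia, and hematologic toxicity that keeps cycle 1 TMZ delivery from exceeding 80% of plan. The lead-in to the non-hematologic list carries no such condition.

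For doubtful cases the same section adds: "The ABTC Central Office, with the Study Chair, will make the final decision". It gives no rule for incomplete CBCs.

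Section 4.1.1 turns DLT counts into decisions. Two of six is the MTD. Two or three of three, or at least three of six, means "MTD exceeded, enter 3 patients at next lower dose/schedule". On evaluability it says: "Patients will be evaluable for the cohort if they have completed at least 80% of their expected dose of pamiparib" in cycle 1; a patient with a DLT needs only one dose. CBCs are not mentioned there.

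The draws are also required independently of the DLT definition: weekly in Sections 4.5.2 and 5.2.1, and when counts are low, under footnote 9 of Section 9.1.1, "CBCs/differentials will be repeated twice a week until counts are recovered".

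**The concern.** A missed draw can hide an event, but it cannot undo one already recorded. An ANC below 500/µL, a platelet count below 25,000/µL or a febrile neutropenia is complete as a DLT when it is seen. For these three criteria the condition therefore adds nothing to the validity of the event. All it can do is remove a DLT from the count, so any error favours accepting the schedule.

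Draw compliance could matter for a patient with no observed DLT, in whom a nadir may have been missed. The evaluability rule does not ask for it there.

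At stake is the TMZ schedule carried into Phase II (39-78 patients in Section 3.1) and into the post-surgical cycles, chosen on at most six patients per level. Hematologic toxicity is the expected risk. Section 2.2 reports that a related study with TMZ 40 mg "found this combination exceeded MTD because of neutropenia and thrombocytopenia". This trial starts at 20 mg, which lowers that risk without removing it.

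**Working it through.** **1. The plan's own figure.** The 2-of-6 rule gives 2/6 = 33.3%, which matches the stated 33% target DLT rate.

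**2. What the condition touches.**

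| Hematologic criterion (Section 5.1) | Established by one observation? | Can a missed recovery draw create it? |
|---|---|---|
| Grade 4 neutropenia | Yes | No |
| Grade 4 thrombocytopenia | Yes | No |
| Grade 3-4 febrile neutropenia | Yes | No |
| TMZ delivery not above 80% of plan | No, depends on length of hold | Yes |

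On the fourth criterion, the Toxicity Management Table in Section 5.2 ends a hold for neutropenia or thrombocytopenia only once the count has recovered to its threshold or baseline. Taking the criterion to mean that 80% or less of planned TMZ was given, the missed doses that trigger it are 6 of 28 (22/28 = 78.6%), 5 of 21 (76.2%), 3 of 14 (78.6%) and 2 of 7 (71.4%). Slipping from twice-weekly to weekly draws can add about 3-4 days to a hold. On the 14- or 7-day schedules that alone could meet the threshold if the days fall on TMZ dosing. The condition does useful work here.

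**3. What happens to the patient whose event is not counted.** Cycle 1 has 2 × 28 = 56 pamiparib doses, and 80% of these is 44.8, so 45 doses, reached on day 23 if none is missed. A patient with a later event is already evaluable, and the uncounted event would be scored as no DLT: 3/6 becomes 2/6, or 2/3 becomes 1/3. A patient held earlier may fall below 80%, would then not be evaluable, and would presumably be replaced. In that case the decision changes only if the replacement has no DLT. The documents do not say which applies, so both are shown.

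**4. Illustrative size.** A schedule is accepted with at most 1 DLT in the first 3 patients and at most 2 in all 6. At counted DLT rate p:

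A(p) = P(0/3) × P(≤2/3) + P(1/3) × P(≤1/3)

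- p = 0.40: 0.216 × 0.936 + 0.432 × 0.648 = 0.482
- p = 0.50: 0.125 × 0.875 + 0.375 × 0.500 = 0.297

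Assumptions, none given in the documents: true DLT rate t; hematologic share h; fraction m of hematologic DLTs voided. Let v = t × h × m. If voided patients are replaced, p = (t − v)/(1 − v). If they are scored as no DLT, p = t − v. Example with t = 0.40, h = 1, m = 0.10: v = 0.04, so p = 0.36/0.96 = 0.375 and A = 0.532 (replaced), or p = 0.36 and A = 0.562 (scored as no DLT).

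| t | h | A, no voiding | m = 2%, replaced | m = 5%, replaced | m = 10%, replaced | m = 10%, no DLT |
|---|---|---|---|---|---|---|
| 0.40 | 1 | 0.482 | 0.492 | 0.506 | 0.532 | 0.562 |
| 0.40 | 0.75 | 0.482 | 0.489 | 0.500 | 0.519 | 0.542 |
| 0.50 | 1 | 0.297 | 0.305 | 0.319 | 0.343 | 0.386 |
| 0.50 | 0.75 | 0.297 | 0.303 | 0.313 | 0.331 | 0.363 |

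The fraction m is applied to all hematologic DLTs. Events under the fourth criterion are not separated out, so the table if anything overstates the part that the fix would change.

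**The case against.** The best case for leaving the text alone has four parts.

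- *Adjudication exists.* Any doubt about a DLT goes to the Central Office, and nothing directs it to discard an observed event. The sentence also says *if*, not *only if*. This stands as mitigation. It leaves the outcome to discretion, though, and the only written guidance points towards not counting.
- *The patient is protected anyway.* Section 5.2 requires a hold and a TMZ reduction for each of the three events whatever the DLT label. Section 11.0 also reports them: "The severity and frequency of toxicity will be tabulated by the tested doses using descriptive statistics". Both are true, but the decision table in Section 4.1.1 uses only the DLT count.
- *The condition has a purpose.* For the TMZ-delivery criterion it does, as shown above. A reader might infer that the condition should be deleted outright. That goes too far, because it could turn a missed appointment into a DLT.
- *The schedule named is narrow.* A reader might infer that any missed draw voids an event. The parenthesis names only the twice-weekly draws, which elsewhere in the protocol follow a low count, while routine weekly draws are set in other sections. The text does not support the broader reading; at most it is unclear which missed draw matters.

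A reader might also infer that the Phase I schedule was chosen on an incomplete count. Nothing in the documents shows that any event was excluded.

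**Conclusion.** Section 5.1 is wrong as written for grade 4 neutropenia, grade 4 thrombocytopenia and grade 3-4 febrile neutropenia. No other section says that such an event counts when the mandated draws were incomplete. The condition is defensible for the TMZ-delivery criterion.

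Severity is minor. For harm to occur, a qualifying event, incomplete mandated draws and an adjudication that discards the event must coincide in one of a few Phase I patients. The documents give no voiding rate, no true DLT rate and no hematologic share, so the size cannot be derived from them. Under assumed voiding of 2-10%, acceptance of a schedule rises by about 0.01 to 0.09, with the upper end requiring 10% voiding, all DLTs hematologic and every voided patient scored as having no DLT. The conclusion itself rests on the wording and on the sensitivity of the 3+3 rule to one event; it does not depend on those figures.

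**What to change.** In Section 5.1, state that any grade 4 neutropenia, grade 4 thrombocytopenia or grade 3-4 febrile neutropenia observed in cycle 1, and at least possibly related to pamiparib or TMZ, counts as a DLT regardless of CBC-schedule compliance. Attach the CBC-schedule condition to the TMZ-delivery criterion alone. Keep the twice-weekly draws as a monitoring instruction. The clinical thresholds and the decision table stay as they are.

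If Phase I has already been run, confirm from the DLT records that no such event was left out on this ground.

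The cost is about one sentence. The observed DLT rate may come out slightly less favourable.

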Grade 4 Hepatic (> 10 x ULN bilirubin)	Permanently discontinue pamiparib (BGB-290) and TMZ.				
	Note: if grade 3 or 4 hyperbilirubinemia is due to indirect (unconjugated) component only, and hemolysis as the etiology has been ruled out per institutional guidelines, then decrease TMZ by 1 dose level and continue treatment at the discretion of the investigator				
Grade 3 Hepatic (> 5 and ≤ 20 x ULN AST and/or ALT)	Hold pamiparib (BGB-290) and TMZ until AST and/or ALT resolved to $\leq 5 \text{ x ULN}$ or baseline.				
	-if \leq 5 x ULN within 14 days, then decrease pamiparib (BGB-290) and TMZ by 1 dose level				
	-if second episode, permanently discontinue pamiparib (BGB-290) and TMZ				
	-If persistent for > 14 days, permanently discontinue pamiparib (BGB-290) and TMZ				
Grade 4 Hepatic (> 20 x ULN AST and/or ALT)	Permanently discontinue pamiparib (BGB-290) and TMZ.				
Grade 3 Renal (> 3-6 x ULN serum creatinine) and	Permanently discontinue pamiparib (BGB-290) and TMZ.				
Grade 4 Renal (> 6 x ULN serum creatinine)					
Serum creatinine 2-3 x ULN	Hold pamiparib (BGB-290) and TMZ until recovery to grade ≤ 1 or baseline.				
	-if resolved \leq 7 days, then maintain dose levels				
	-if resolved > 7 days, then decrease TMZ by 1 dose level				

ABTC # 1801

NCI # ABTC-1801

PI: [name]

Toxicity	Actions
Hematological toxicity	
Grade 3 Thrombocytopenia (platelets < 50,000 ≥ 25,000/µL)	Hold pamiparib (BGB-290) and TMZ until recovery to platelets \geq 100000 µl or baseline.
	-if resolved \leq 7 days, then maintain dose levels
	-if resolved > 7 days, then decrease TMZ by 1 dose level
Grade 4 Thrombocytopenia (platelets < 25,000/µL)	Hold pamiparib (BGB-290) and TMZ until resolved to platelets ≥ 100000 µl or baseline and decrease TMZ by 1 dose level
Grade 3 Neutropenia (neutrophils < $1,000 \ge 500/\mu$ L)	Hold pamiparib (BGB-290) and TMZ until resolved to $\geq 1500/\mu l$ or baseline
	-if resolved \leq 7 days, then maintain dose levels
	-if resolved > 7 days, then decrease TMZ by 1 dose level
Grade 4 Neutropenia (neutrophils < 500/µL)	Hold pamiparib (BGB-290) and TMZ until resolved to Grade ≤ 1 or baseline and decrease TMZ by 1 dose level
Febrile neutropenia (ANC < 1,000 with single temperature of > 38.3° C or sustained temperature of > 38° C for > 1 hour)	Hold pamiparib (BGB-290) and TMZ until resolved and decrease TMZ by 1 dose level
Grade 2 Anemia (Hb < 10 - 8 g/dL)	First occurrence: continue dosing at current dose level.
	Second and subsequent occurrences: hold pamiparib (BGB-290) and TMZ until resolved to \leq Grade 1 or baseline:
	-if resolved \leq 14 days, then maintain dose levels
	-if resolved > 14 days, then ↓ TMZ by 1 dose level and continue pamiparib (BGB-290) at same dose
Grade 3 Anemia (Hb < 8 g/dL)	Hold pamiparib (BGB-290) and TMZ until resolved to Grade ≤ 1 or baseline
	-if resolved \leq 7 days, then maintain dose levels
	-if resolved > 7 days, then decrease TMZ by 1 dose level

NCI # ABTC-1801

Toxicity	Actions
Grade 4 Anemia (life threatening consequences; urgent intervention indicated)	Hold pamiparib (BGB-290) and TMZ until resolved to Grade ≤ 1 or baseline and
	decrease TMZ by 1 dose level

5.2.1 Dose Modification for Temozolomide and Pamiparib (BGB-290)

Dose reductions are required as indicated in the toxicity table above for any dose limiting toxicity (as defined in Section 5.1). Dosing will stop until the DLT has resolved to \leq grade 1 [or tolerable grade 2 for non-hematologic toxicity] or \leq baseline. The maximum length of time that pamiparib (BGB-290) and TMZ can be held is 21 days, or as stipulated in the table. After resolution, the dose of TMZ will be modified as stipulated below, with a maximum of 2 dose reductions. If treatment-related toxicity is not resolved in \leq 21 days (or as stipulated), the patient will be considered for monotherapy with pamiparib (BGB-290). If there is any question, the ABTC Central Office and the study chair should be contacted.

Dose level	Temozolomide dose	Dose reduction 1	Dose reduction 2
1 (starting dose)	20 mg QD Days 1-28	20 mg QD Days 1-21	20 mg QD Days 1- 14
-1	20 mg QD Days 1-21	20 mg QD Days 1-14	20 mg QD Days 1-7
-2	20 mg QD Days 1-14	20 mg QD Days 1-7	Either off study or pamiparib (BGB- 290) alone
-3	20 mg QD Days 1-7	Either off study or pamiparib (BGB-290) alone	N/A

TMZ Dose Reduction Schedule

ABTC # 1801

Blood counts will be evaluated weekly. Within -5 days prior to first dose of each cycle the patient must have an ANC \geq 1500/ul and platelet count \geq 100,000/ul. On Day 1 of each cycle (within -5 days) all **non-hematological** toxicity grade 3 or 4 (except for alopecia, nausea and vomiting) must have resolved (CTCAE grade \leq 1). If toxicity persists, treatment should be delayed by one week for up to 3 consecutive weeks. If after 3 weeks of delay all toxicity has still not resolved then any further treatment with temozolomide should be stopped (patient is off treatment).

If pamiparib (BGB-290) must be modified as stipulated in the Toxicity Management Table, the dose of pamiparib (BGB-290) will be modified as shown below, with a maximum of 2 dose reductions.

PI: [name]

NCI # ABTC-1801

PI: [name]

Dose Level	Pamiparib (BGB-290)					
Starting dose	60 mg b.i.d.					
First dose reduction	40 mg b.i.d.					
Second dose reduction	20 mg b.i.d.					

Pamiparib (BGB-290) Dose Reduction Schedule

